4.4.6. Blinding

The first vaccination (H3N2 M2SR or saline placebo) will be prepared by the licensed pharmacist and administered by an unblinded study vaccine administrator. All follow-up safety and efficacy evaluations will be performed by blinded clinic staff.

The pharmacist at each site will refer to the Treatment Key provided for the trial by the SDCC to determine the treatment for the subjects. The pharmacist will maintain an open label code (provided by the SDCC) under locked/secured conditions and will follow the randomization code. The study products are identical in appearance.

The protocol contains no explicit provisions for emergency unblinding. According to DMID policy, the study medical monitor responds to requests for emergency unblinding and instructs the SDCC to release treatment codes only if necessary to ensure that the subject receives appropriate clinical care.

4.4.7. Prior and Concomitant Therapy

Concomitant medications will include all current medications and medications taken in the 30 days prior to signing the informed consent form through approximately 21 days after the first study vaccination, early termination or unscheduled visits (if prior to 21 days after the first study vaccination), whichever occurs first. Prescription and over-the-counter drugs will be included as well as herbals, vitamins, and supplements. In addition, receipt of non-study influenza vaccines will be solicited through approximately 21 days after the first study vaccination. The use of aspirin or salicylate containing products will be solicited from 30 days prior to the first vaccination through 21 days after the last vaccination.

4.4.8. Treatment Compliance

All subjects are to receive a single intranasal dose of either H3N2 M2SR or saline placebo administered in the clinic as the first vaccination. All subjects are to receive a single QIV vaccination approximately 3 months after the first vaccination.

4.5. Immunogenicity and Safety Variables

See [Table 2](#) for a schedule of study procedures.

4.5.1. Immunogenicity Variables

Individual HAI and Neut titer results will be reported by the laboratory at St. Louis University for the H3N2 M2SR-like (A/Brisbane/10/2007) and H3N2 QIV-like viruses (A/Singapore/INFIMH-16-0019/2016 and cell culture-propagated A/North Carolina/04/2016 for 2018/2019 and any additional strains specific to the 2019/2020 QIV). The HAI assay for the A/North Carolina/04/2016 strain only will be tested using both turkey and guinea pig red blood cells (RBC) separately, both with and without oseltamivir. All other strains will be tested using turkey RBC without oseltamivir, and these results from these conditions will be used in grouped displays of QIV-like results. For analysis, the geometric mean (calculated on natural log scale) of repeated results for each subject at each visit will be computed and used as the response for all subsequent calculations. The variation arising from multiple measurements for an individual at a single time point is not used in subsequent calculations. See [Section 3.3](#) for definitions of derived variables for the analysis of HAI and Neut data.

The laboratory at Saint Louis University will also provide individual titer results for nasal sIgA against the H3N2 M2SR-like and H3N2 QIV-like viruses and total sIgA, as well as individual H3 HA-specific (H3 M2SR-like and QIV-like viruses) For analysis, the geometric mean (calculated on natural log scale) of repeated results for each subject at each visit will be computed and used as the response for all subsequent calculations. The variation arising from multiple measurements for an individual at a single time point is not used in subsequent calculations. The frequency of conserved internal viral protein-specific (H3 M2SR-like and QIV-like viruses) IFN- γ T Cells per million PBMC as measured by ELISPOT will also be reported. See Section 3.3 for definitions of derived variables for the analysis of sIgA and IFN- γ T Cell results.

4.5.2. Safety Variables

Safety will be assessed by the frequency and severity of:

1. SAEs occurring from the time of the first study vaccination through 12 months after the first vaccination.
2. AESIs (wheezing, otitis media) and NOCMCs occurring from the time of the first study vaccination through 3 months after the first vaccination.
3. Solicited Adverse Events – reactogenicity events occurring from the time of experimental (first) study vaccination through 7 days after the first study vaccination.
4. Unsolicited Non-Serious Adverse Events –non-serious AEs occurring from the time of the first study vaccination through approximately 21 days after the first study vaccination.
5. Clinical safety laboratory AEs occurring at approximately 7 days after the first vaccination. Parameters to be evaluated include a WBC, HGB, Platelet Count, ALT, AST, Serum Creatinine, Ferritin level, PT and aPTT. HGB will also be repeated at Day 22 if there is a drop in HGB level from screen to Day 8 of > 0.5 g/dL or results are < lower limits of normal. If unable to collect at Day 22, collect at Day 57. If drawn at Day 22 and the results are still low, repeat at Day 57. If HGB results are still low at Day 57, no further PBMC collection will be done. HGB and Ferritin level will be drawn at Day 113. If the ferritin is < 15 ng/mL and/or the HGB is less than the lower limits of normal, will recommend follow-up with primary care provider for consideration of multivitamins with iron.

Grading scales for injection site and systemic solicited reactions, respiratory tract assessments, AESI, vital signs, and clinical laboratory parameters are provided in [Table 6](#), [Table 7](#), [Table 8](#), [Table 9](#), [Table 10](#), and [Table 11](#).

5. SAMPLE SIZE CONSIDERATIONS

This study is planned to enroll approximately 25 subjects in each treatment arm (Table 1). The sample size for this study was selected to obtain preliminary estimates in a pediatric population. While this study is not designed to test any specific null hypothesis, the following tables illustrate the precision and power available for select estimates and comparisons of interest.

Table 3 indicates the probability of observing one or more safety events, such as solicited local or systemic reactogenicity events or an unsolicited AE of a particular type, for a single treatment arm (N=25), and for all enrolled subjects (N=50).

Table 4 illustrates the minimum detectable differences in the proportion of subjects responding (e.g., attaining seroconversion or a titer $\geq 1:40$) between two treatment arms for a range of possible response rates in the comparator arm, using a Chi-Square Test and $\alpha = 0.05$. In a Previous DMID trial (12-0016) in this population approximately 8% of subjects did not have available immunogenicity data at Day 42. Table 4 is presented for the planned enrollment (N = 25 per group) and accounting for 10% drop out (N = 22 per group).

6. GENERAL STATISTICAL CONSIDERATIONS

6.1. General Principles

Unless otherwise specified, continuous variables will be summarized using the following descriptive statistics: n (non-missing sample size), mean, standard deviation, median, maximum and minimum. For post-baseline visits, fold rise from baseline will be calculated. Unless otherwise specified, confidence intervals for means (arithmetic or geometric) will be calculated using the student's t distribution with confidence level $\alpha=0.05$ (95% confidence). P-values for spearman correlations will be calculated using the student's t distribution testing the hypothesis that the two variables tested are not correlated. The frequency and percentages (based on the non-missing sample size) of observed levels will be reported for all categorical measures. In general, all data will be listed, sorted by site, study group and subject, and when appropriate by visit number within subject. All summary tables will be structured with a column for each study group in the order presented in [Table 1](#) and will be annotated with the total population size relevant to that table/treatment, including any missing observations.

6.2. Timing of Analyses

The interim analysis will be performed after all 19 subjects enrolled in 2018 have completed the Day 113 visit and HAI, MN, and sIgA data are available. The final analysis will be performed when all enrolled subjects have completed the Day 366 visit, the clinical database has been cleaned, monitored, and locked, and data is available for all secondary immunogenicity measures. Exploratory immunogenicity assays will be performed pending the results observed for the secondary outcome measures as described in [Section 8.3](#). Analyses of the exploratory outcome measures will be described in addendum to this SAP.

6.3. Analysis Populations

Demographic and baseline characteristics will be presented for all enrolled subjects. All safety summaries will be presented for the safety population ([Section 6.3.3](#)). Secondary immunogenicity measures will be presented for the Per Protocol (PP) and modified intent-to-treat (mITT) populations.

A tabular listing of all subjects, visits, and observations excluded from analyses will be provided in the CSR ([Listing 7](#)).

6.3.1. Modified Intention-to-Treat (mITT) Population

The modified intent-to-treat (mITT) population includes all subjects who received at least one dose of study vaccine and contributed both pre- and at least one post-study vaccination sample for immunogenicity testing for which valid results were reported. Available valid results will be assessed separately for each assay (HAI, Neutralizing antibody, sIgA, frequency IFN- γ T-cells). For analyses using the mITT population, subjects will be grouped based on randomized treatment arm.

6.3.2. Per Protocol Population

The per protocol (PP) population includes all subjects in the mITT subset with the following exclusions:

- Data from all available visits for subjects found to be ineligible at baseline.
- Data from all visits subsequent to major protocol deviations, such as:
 - Second study vaccination not received,

- Second study vaccination received out of window,
- Receipt of non-study licensed live or inactivated vaccine within 30 days before or after each study vaccination.
- Receipt of influenza vaccine (live or inactivated) within 6 months prior to 30 days after for analyses using the PP population, subjects will be grouped based on study vaccinations received.

6.3.3. Safety Population

The Safety Analysis population includes all subjects who received one dose of M2SR vaccine. For analyses using the safety population, subjects will be grouped based on study vaccinations received.

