### Investigational Vaccine (Bris10 M2SR)

Visually inspect the study vaccine (Bris10 M2SR, vaccine diluent and placebo [normal saline]) upon receipt and prior to preparation and use. If the study vaccine appear(s) to have been damaged, contaminated or discolored, or if there are any concerns regarding its integrity, do NOT use the affected study vaccine. The affected study vaccine must be quarantined and labeled as “Do Not Use (until further notice).” The Site Principal Investigator or responsible person should immediately contact the DMID Product Support Team at [[contact]](mailto:[contact]) and DMID Clinical Project Manager for further instructions before any additional study vaccinations are administered. Based on the information collected, DMID and/or the manufacturer will determine whether the affected study vaccine can be used. If it cannot be used, the site will receive specific final disposition instructions from DMID. If the study vaccine is unusable, the participating VTEU site’s pharmacist will prepare another dose. Replacement vials may be requested by contacting DMID. Additional instructions for quarantine and DMID contact information are provided in the protocol-specific MOP.

Depending on randomization, each subject will be randomized to receive a one-time intranasal administration of a priming vaccine either:

Bris10 M2SR vaccine at  $10^8$  virus particles OR placebo (normal saline) at Day 1 followed by a one-time intramuscular administration of quadrivalent inactivated vaccine at Day 92.

The Bris10 M2SR vaccine will be diluted on-site as needed by the Pharmacist. The Pharmacist will also fill vaccine and placebo into nasal spray devices.

Study vaccine administration will be performed by an unblinded study vaccine administrator who is credentialed to administer vaccines and may also participate in dose preparation, but will not be involved in study-related assessments or have subject contact for data collection following study vaccine administration. On the assigned days, each dose of study vaccine or placebo will be administered to subjects via the nasal spray devices into each nostril.

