#### **11.4.1. Analysis Populations**

The Safety Analysis population includes all subjects who received at least one dose of study vaccine.

The modified intent-to-treat (mITT) population includes all subjects who received at least one dose of study vaccine and contributed both pre- and at least one post-study vaccination venous blood samples for immunogenicity testing (HAI antibody assays) for which valid results were reported. For analyses using the mITT population, subjects will be grouped based on randomized treatment arm.

The per protocol (PP) population includes all subjects in the mITT subset with the following exclusions:

- Data from all available visits for subjects found to be ineligible at baseline.
- Data from all visits subsequent to major protocol deviations, such as:
  - Second study vaccination not received,
  - Second study vaccination received out of window,
  - Receipt of non-study licensed live or inactivated vaccine within 30 days prior to the first study vaccination,
  - Receipt of influenza vaccine (live or inactivated) within 6 months prior to the first study vaccination.
- Receipt of immunosuppressive therapy (e.g., corticosteroids)
  - Receipt of aspirin or salicylate-containing products
  - Receipt of antiviral therapy
- Data from any visit that occurs substantially out of window, such that in the opinion of the study investigator could affect the scientific goals of this protocol.

For analyses using the PP population, subjects will be grouped based on study vaccinations received.

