4. INVESTIGATIONAL PLAN

4.1. Overall Study Design and Plan

This is a Phase I double-blind, randomized, placebo-controlled study in 50 healthy adolescents and children, 9-17 years of age, who are in good health and meet all eligibility criteria. The study is designed to assess the safety and immunogenicity of a prime-boost regimen of H3N2 M2SR intranasal influenza vaccine followed by licensed inactivated QIV boost administered IM. Group A will receive one dose of M2SR intranasally on Day 1 and one dose of QIV on Day 92. Group B will receive one dose of saline intranasally on Day 1, and one dose of QIV on Day 92. See [Table 1](#) for the randomization scheme for this trial.

The two study arms will be enrolled and vaccinated concurrently. Enrollment was paused in November 2018 until the spring of 2019 to ensure all subjects received seasonal QIV vaccine prior to the beginning of the influenza season. An interim analysis of safety and immunogenicity data through the Day 113 visit will be performed for all subjects enrolled in 2018. For details on changes to the study design and planned analyses see [Section 12](#).

Reactogenicity will be measured by the occurrence of solicited upper respiratory (local) and systemic reactions from the time of the experimental (first) study vaccination through 7 days after vaccination and a respiratory tract assessment at 7 days post vaccination (Visit 02). Unsolicited non-serious AEs will be collected from the time of the first study vaccination through approximately 21 days after the first study vaccination. SAEs will be collected from the time of the first study vaccination throughout the entire study. AESIs (wheezing and otitis media) and NOCMC will be documented and reported from the time of first study vaccination through approximately 3 months after first study vaccination.

Immunogenicity testing will include performing HAI, neutralization, and nasal secretory IgA (sIgA) assays for secondary endpoints. If significant responses are observed to be induced by H3N2 M2SR vaccination, then HA/NA ELISA, IFN- γ ELISPOT and CFSE dilution/ICS assays will also be performed (see [Section 8.3](#) for further details). If performed, analyses for these assay results will be described in an addendum for this SAP.

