4.4.3. Method of Assigning Subjects to Treatment Groups (Randomization)

Enrollment/randomization will be performed through the enrollment module in the electronic data capture system, maintained by the SDCC.

Eligible subjects will be randomized and assigned in a 1:1 ratio to receive intranasal H3N2 M2SR or saline placebo, with stratification by site. The randomization is based on a variable blocked scheme to provide an approximately balanced allocation to the treatment groups during the study.

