9. SAFETY EVALUATION

All summaries and analysis of safety data will be presented for the Safety Analysis Population. Safety summaries will be presented overall and stratified by study group. Note that solicited and unsolicited non-serious adverse events are reported following first vaccination only; as such displays are limited to first vaccination.

Listings will be sorted by study group subject ID, parameter (if applicable), and visit.

Continuous variables will be summarized using the following descriptive statistics: n (non-missing sample size), mean, standard deviation, median, maximum and minimum. All categorical measures will be summarized by the frequency and percentages (based on the non-missing sample size) of observed levels.

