Table 11: Laboratory Adverse Event Grading Scale (Chemistry)

Chemistry Parameter	Mild (Grade 1)	Moderate (Grade 2)	Severe (Grade 3)
ALT	1.25 – < 2.5 x ULN	\geq 2.5 – <5.0 x ULN	\geq 5.0 x ULN
AST	1.25 – < 2.5 x ULN	\geq 2.5 – <5.0 x ULN	\geq 5.0 x ULN
Creatinine mg/dL	1.1 – 1.3 x ULN	>1.3 – 1.8 OR Increase to 1.3 to < 1.5 x subject's baseline	>1.8 x ULN OR Increase to \geq 1.5 x subject's baseline

14.1 Description of Study Subjects**14.1.1 Disposition of Subjects****Table 12: Subject Disposition by Treatment Group – All Enrolled Subjects***

Subject Disposition	M2SR (N=X)		Placebo (N=X)		All Subjects (N=X)	
	n	%	n	%	n	%
Screened	--	--	--	--	x	--
Enrolled/Randomized	x	100	x	100	x	100
Received First Vaccination	x	xx	x	xx	x	xx
Received Second Vaccination	x	xx	x	xx	x	xx
Received All Scheduled Vaccinations ^a	x	xx	x	xx	x	xx
Completed Final Blood Draw (Study Day 113)	x	xx	x	xx	x	xx
Completed Follow-up (Study Day 366) ^a	x	xx	x	xx	x	xx
Completed Per Protocol ^b						

Note: N=All Enrolled Subjects
^a Refer to Listing 16.2.1 for reasons subjects discontinued or terminated early.
^b Refer to Listing 16.2.3 for reasons subjects are excluded from the Analysis populations .

Table 13: Analysis Populations by Study Group – All Enrolled Subjects

Analysis Populations	Reason Subjects Excluded	M2SR (N=X)		Placebo (N=X)		All Subjects (N=X)	
		n	%	n	%	%	n
Safety Population	Did not receive first study vaccination.	x	xx	x	xx	x	xx
Modified Intent-to-Treat Population	Any Reason						
	Did not receive first study vaccination.						
	No Baseline Sample						
	No Post-Baseline Sample						
	No Baseline HAI Results Reported						
	No Post-Baseline HAI Results Reported						
Per Protocol Population (All Visits)	Any Reason						
	Did not receive first study vaccination.						
	No Baseline Sample						
	No Post-Baseline Sample						
	No Baseline HAI Results Reported						
	No Post-Baseline HAI Results Reported						
Per Protocol Population (Day 8)	Any Reason						
	Visit not conducted						
	Sample not collected						
	Result not reported						
	Receipt of live or inactivated vaccine						
	Receipt of immunosuppressive therapy						
	Visit Out of Window by >1 Day						
	Other reason						
Per Protocol Population (Day 22)	Any Reason						
	Sample not collected						
	Result not reported						
	Receipt of live or inactivated vaccine						
	Receipt of immunosuppressive therapy						
	Visit Out of Window by >1 Day						
Other reason							

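### SAP 6.3.3 defines the Safety population by receipt of M2SR, which literally excludes every correctly dosed placebo subject and contradicts both the protocol and the rest of the SAP

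*SAP*

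**What the plan says.** SAP 6.3.3 reads: "The Safety Analysis population includes all subjects who received one dose of M2SR vaccine". Its next sentence sets the grouping: "For analyses using the safety population, subjects will be grouped based on study vaccinations received".

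The population governs all safety reporting. SAP Section 9 states: "All summaries and analysis of safety data will be presented for the Safety Analysis Population". SAP 6.3 says the same, and Section 9 adds that results are shown for each study group as well as for both combined.

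Protocol 11.4.1 has a different definition: "The Safety Analysis population includes all subjects who received at least one dose of study vaccine". The protocol's use of study vaccine includes the saline; its preparation instructions in Section 6.2 say: "Visually inspect the study vaccine (Bris10 M2SR, vaccine diluent and placebo [normal saline]) upon receipt".

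On who receives what, SAP 4.4.3 has subjects "assigned in a 1:1 ratio to receive intranasal H3N2 M2SR or saline placebo", and SAP 4.1 says: "Group B will receive one dose of saline intranasally on Day 1, and one dose of QIV on Day 92".

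In SAP Table 13, the only reason listed for exclusion from the Safety population is "Did not receive first study vaccination". Table 44 is reserved for placebo recipients within the Safety population. Table 41 shows the difference between arms in the proportion of subjects with each solicited event.

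**The concern.** All four primary endpoints are safety endpoints: solicited reactions, unsolicited adverse events, serious adverse events, and special-interest events with new chronic conditions. SAP 2.1 says the analyses are to assess safety against saline placebo. A population rule that admits only M2SR recipients takes away that comparator.

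The comparator matters here. Runny nose, cough and headache are common in children whatever they are given. SAP Section 12 also reports consistent hemoglobin falls after the first vaccination among the 2018 enrollees, and SAP 4.3 says the protocol was amended partly to reduce the blood collected. Placebo children bled on the same schedule are the natural reference for separating a vaccine effect from a blood-draw effect. The hemoglobin displays (Tables 60, 61, 66 and 67) would lose that reference under the literal definition.

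The wording is also hard to read as shorthand. The mITT definition in SAP 6.3.1 refers to study vaccine generally, so a placebo child with valid samples is in the mITT population but, literally, not in the Safety population.

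**Working it through.** **1. The plan's own safety figure.** SAP and protocol Table 3 give the chance of seeing at least one event, for N=25 (one arm) and N=50 (all enrolled). The formula is 1 − (1 − p)^N.

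| True event rate p | N=25 computed | N=25 printed | N=50 computed | N=50 printed |
|---|---|---|---|---|
| 10% | 92.8% | 93 | 99.5% | >99 |
| 1% | 22.2% | 22 | 39.5% | 40 |
| 0.1% | 2.5% | 3 | 4.9% | 5 |
| 0.01% | 0.25% | <1 | 0.5% | <1 |

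The table reproduces to within one percentage point. Its second column treats all 50 subjects as contributing safety data.

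**2. Who meets each definition.** Inputs: 25 planned subjects per arm (SAP Section 5 and Table 1), allocation 1:1 (SAP 4.4.3), no M2SR in Group B (SAP 4.1). Assume every planned subject receives the assigned first dose.

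- SAP 6.3.3 as written: 25 M2SR + 0 placebo = 25.
- Protocol 11.4.1, with placebo counted as study vaccine: 25 + 25 = 50.
- Excluded by the SAP wording: 50 − 25 = 25, or 25/50 = 50%, all of them placebo.

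**3. What the smaller N changes.** For the combined-arm summaries, the chance of seeing at least one event falls from the N=50 to the N=25 column: 99.5% to 92.8% at a 10% rate, 39.5% to 22.2% at 1%, 4.9% to 2.5% at 0.1%. The M2SR arm has 25 subjects under either definition, so estimates within that arm do not change. The real loss is the comparator.

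**4. Effect on the displays if 6.3.3 is applied literally.**

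- By-arm summaries (Tables 38–42, 45–47 and 54–67): the placebo columns or rows have N=0. Tables 14, 19 and 68 also set N to the Safety population in their notes.
- Table 44: empty.
- Table 41: a difference and its interval need a proportion in each arm. With a placebo denominator of 0, neither can be computed.
- Table 43: unchanged, because it shows M2SR recipients only.
- Tables 48–53: subject-level listings with no arm columns, but titled for the Safety population, so placebo children's entries would literally be left out.
- Listings 11–15 in Appendix 3: no Safety-population restriction is stated, so individual placebo events and laboratory results would still appear.
- Immunogenicity in the mITT and PP populations, and demographics in enrolled subjects (Tables 17 and 18): unaffected.

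**5. Is it a deliberate change?** SAP Section 12 lists changes to conduct and planned analyses. It records none to the Safety population.

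**The case against.** The strongest reply is that this is one bad sentence in a plan that otherwise plainly includes placebo. The grouping rule in the same paragraph would have no purpose for first-dose safety if everyone had received M2SR. Section 9, Table 13, Table 41 and Table 44 all presuppose two arms, as does the purpose stated in SAP 2.1. A programmer would notice an empty Table 44 at once. The study is descriptive, with no formal hypothesis, and neither data collection nor sample size is touched.

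Most of this stands. A reader might infer that the SAP as a whole drops the control arm, or that every primary safety table loses it. The documents do not support that: the SAP contradicts itself, and not every safety table has a placebo entry to lose. Nor would all placebo safety data disappear, since the individual listings would still show them. Table 41 is the only between-arm difference planned in the SAP's safety section; the rest is by-arm description. The placebo arm is also not the only basis for attribution, because the plan has investigator causality assessments and pre-dose symptom grading.

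A reader might also infer that dosing errors in both directions would be mishandled. They would not. A child assigned placebo but given M2SR is included and grouped as M2SR, exactly as under the corrected wording. A child assigned M2SR but given only saline is excluded for the same reason as any saline recipient, so this is not a separate defect.

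What does not stand is the idea that the shells settle the matter. The protocol assigns the SAP to define the analyses in the study report, and SAP Section 1 requires any departure from the SAP to be described and justified. An analyst must therefore either follow 6.3.3 and lose placebo, or follow the shells and depart from the written definition. Membership of the population for the primary objective should not be left to that choice.

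**Conclusion.** The definition in SAP 6.3.3 is wrong as written. It conflicts with Protocol 11.4.1 and with at least four other elements of the SAP: the grouping rule, reporting by study group, the Table 13 exclusion reason and Table 44. Its literal effect is to admit 25 of 50 planned subjects and none on placebo, assuming planned enrollment is met and all first doses are given as assigned. The by-arm safety summaries would then have no placebo data, and Table 41 could not be produced.

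This is most likely a drafting slip, and an actual single-arm safety report is unlikely. It still needs correction, because the sentence is the governing definition for the sole primary objective and nothing in the SAP says which of the conflicting statements prevails.

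**What to change.** Replace the text of SAP 6.3.3 with:

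> The Safety population includes all subjects who received the first study vaccination (M2SR or placebo), grouped by the first product actually received.

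This agrees with SAP Table 13. It also agrees with Protocol 11.4.1, because under the schedule a subject's first dose of any study product is the first study vaccination. Naming the first product makes the grouping unambiguous, since both arms later receive QIV.

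The cost is one sentence in the SAP. It needs no new data and no change to trial conduct, sample size or table shells. It should be made before any unblinded safety analysis, so that population membership is fixed in writing in advance.
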